The trial will be conducted in accordance with International Conference on Harmonisation **Good** Clinical Practice (ICH GCP) and applicable United States (US) Code of Federal Regulations (CFR). The Principal Investigator will assure that no deviation from, or changes to the protocol will take place without prior agreement from the Investigational New Drug (IND) sponsor, funding agency and documented approval from the Institutional Review Board (IRB), except where necessary to eliminate an immediate hazard(s) to the trial participants. All personnel involved in the conduct of this study have completed Human Subjects Protection and ICH GCP Training.

The protocol, informed consent form(s), recruitment materials, and all participant materials will be submitted to the IRB for review and approval. Approval of both the protocol and the consent form must be obtained before any participant is enrolled. Any amendment to the protocol will require review and approval by the IRB before the changes are implemented to the study. All changes to the consent form will be IRB approved; a determination will be made regarding whether a new consent needs to be obtained from participants who provided consent, using a previously approved consent form.

1 PROTOCOL SUMMARY

1.1 SYNOPSIS

Title: Ulipristal Acetate for use in early pregnancy loss: A Phase 2 pilot feasibility

study

Study Description: We investigate the feasibility of using 90mg ulipristal acetate, a selective

progesterone receptor agonist, as an adjunct to 800mcg vaginal

misoprostol for the medical management of early pregnancy loss. Patients will be followed to assess effective treatment of early pregnancy loss, additional interventions needed, side effects, adverse events and patient

acceptability.

Objectives: Primary Objective:

To assess if 90mg ulipristal acetate as an adjunct to 800mcg vaginal misoprostol is a feasible method for medical management of early

pregnancy loss.

Secondary Objectives:

To evaluate if participants taking ulipristal acetate plus misoprostol

achieve complete resolution of early pregnancy loss.

To investigate if patients using ulipristal acetate plus misoprostol have side

effects or adverse events when used for early pregnancy loss.

To identify if patients find ulipristal acetate and misoprostol an acceptable

treatment for early pregnancy loss.

Outcomes: Primary Feasibility Outcome Variables:

- Recruitment

- Adherence

- Retention

Secondary Outcome Variables:

- Absence of gestational sac on transvaginal ultrasound following study intervention
- Side effects/adverse events following study intervention
- Patient acceptability of study intervention

UPA for EPL
Protocol 1.0

Version 4.0

January 2022

Study Population: Participants eligible for the study include women over age 18 presenting

with a non-viable pregnancy between 5- and 12-weeks gestation or an anembryonic gestation and desiring medical management. Participants will be excluded if they are hemodynamically unstable, desire non-medical

management, present with an incomplete or inevitable abortion,

contraindication or allergy to the study medications, evidence of a viable intrauterine pregnancy, ectopic pregnancy or pregnancy with an IUD in place, evidence of a pelvic infection, anemia with a hemoglobin less than 9.5g/dL, known cardiovascular disease or known clotting or bleeding

disorder.

Phase: 2

Description of

Sites/Facilities Enrolling

Participants:

All study activities will take place at University of North Carolina-Chapel Hill. Participants will be recruited from OBGYN clinics and the Emergency Department following diagnosis of early pregnancy loss on viability scan. All follow up study activities will take place at UNC Chapel Hill Family

Planning Clinic.

Description of Study Intervention:

Ulipristal acetate is a selective progesterone receptor modulator that is currently FDA approved for the use of emergency contraception. Three 30mg tablets will be administered orally for a total dose of 90mg.

[figure not shown]
Participants will be instructed to self-administer 800mcg of misoprostol 6 to 18 hours after receiving ulipristal acetate as per the standard of care for early pregnancy loss management. Participants will be followed for

resolution of their early pregnancy loss.

Study Duration: 2 years **Participant Duration:** 1 month

1.2 SCHEMA

UPA for EPL Flow Diagram

1.3 SCHEDULE OF ACTIVITIES (SOA)

Procedures	Screening Visit 1, Day 0	Enrollment/Baseline Visit 1, Day 0	At Home Day 0	Study Visit 2 Day 3 +/- 1day	Study Visit 3 Day 8 +/- 1 day	Lab Testing Day 14 +/- 1 day	Study Visit 4 Day 30 +/- 7 days
Eligibility criteria	Х						
Informed consent	Х						
Demographics questionnaire	Х						
Administer UPA		Х					
Patient self-administers			Х				
misoprostol							
Physical exam	Х						
Vital signs	Х			Х	Х		
Hemoglobin and ABO/Rh testing	Х						
Liver function testing	Х					Х	
Adverse event review and evaluation	Х			х	Х		Х
Radiologic/Imaging assessment	Х			Х	Х		
Treatment success questionnaire completed by MD				Х	Х		
Offer additional intervention if needed if gestational sac still present				Х	Х		
Additional treatment questionnaire							Х
Side effects and adverse events questionnaire				х	х		Х
Patient acceptability questionnaire							Х

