- Participant is screened for eligibility by the study coordinator and offered admission to study if eligible
 - Review of radiologic imaging to confirm early pregnancy loss based on eligibility criteria
 - Review of physical exam findings and vital signs (heart rate, blood pressure, temperature) to ensure that patient is hemodynamically stable and not having an inevitable or incomplete abortion based on eligibility criteria
- Participant reviews and signs informed consent and HIPAA authorization form
- Participant completes paper baseline demographic questionnaire
- Participant will have hemoglobin, ABO/Rh status and liver function testing (ALT, AST, total bilirubin) if not already performed by primary OBGYN

 Participant takes 90mg ulipristal acetate with study team; given prescription for 800mcg misoprostol to take at home

Visit 2 (Day 3 ± 1 day):

- Participant returns to UNC Family Planning Clinic
- Participant has vital signs checked by RN at clinic
- Participant fills out questionnaire regarding bleeding symptoms and any side effects or adverse
 events after taking the ulipristal acetate and misoprostol, including reporting time and route of
 administration of misoprostol at home
- Participant has a transvaginal ultrasound completed by the principal investigator to ensure that the pregnancy has passed (no gestational sac visualized on ultrasound)
- If pregnancy is still in the uterus, patient will be offered surgical management, medical management (an additional dose of misoprostol 800mcg), or expectant management

Visit 3 (Day $8 \pm 1 \text{ day}$):

- Participant will only attend this visit if a gestational sac was still present on ultrasound on Visit
 2 and patient opted for medical management or expectant management. If gestational sac is absent at Visit 2, participant will not need Visit 3. All participants will complete Visit 4.
- Participant returns to UNC Family Planning Clinic
- Participant has vital signs checked by RN at clinic
- Participant fills out questionnaire regarding bleeding symptoms and any side effects or adverse events after taking the ulipristal acetate and misoprostol
- Participant has transvaginal ultrasound completed by the principal investigator to ensure that the pregnancy has passed (no gestational sac visualized on ultrasound)
- If pregnancy is still in the uterus, patient will be offered surgical management, medical management (if patient did not receive additional misoprostol at Visit 2), or expectant management

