8.3.4 TIME PERIOD AND FREQUENCY FOR EVENT ASSESSMENT AND FOLLOW-UP

The occurrence of an adverse event (AE) or serious adverse event (SAE) may come to the attention of study personnel during study visits and interviews of a study participant presenting for medical care, or upon review by a study monitor.

All AEs including local and systemic reactions not meeting the criteria for SAEs will be captured on the appropriate case report form (CRF). Information to be collected includes event description, time of onset, clinician's assessment of severity, relationship to study product (assessed only by those with the training and authority to make a diagnosis), and time of resolution/stabilization of the event. All AEs occurring while on study must be documented appropriately regardless of relationship. All AEs will be followed to adequate resolution.

Any medical condition that is present at the time that the participant is screened will be considered as baseline and not reported as an AE. However, if the study participant's condition deteriorates at any time during the study, it will be recorded as an AE.

Changes in the severity of an AE will be documented to allow an assessment of the duration of the event at each level of severity to be performed. AEs characterized as intermittent require documentation of onset and duration of each episode.

The study sponsor will record all reportable events with start dates occurring any time after informed consent is obtained until 7 (for non-serious AEs) or 30 days (for SAEs) after the last day of study participation. At each study visit, the investigator will inquire about the occurrence of AE/SAEs since the last visit. Events will be followed for outcome information until resolution or stabilization.

All participants in the study will have notation on their UNC EPIC chart to alert the research staff if the patient is seen for any possible adverse event. Patients will be assessed for adverse events at their telephone follow up 30 days after study intervention. Solicited information on adverse events will include increased bleeding requiring hospital admission or blood transfusion and infection requiring hospital admission or IV antibiotics. All other adverse events will be identified based on unsolicited questioning during this telephone visit.

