9.4.3 ANALYSIS OF THE SECONDARY OUTCOME VARIABLE(S)

- Resolution of EPL
 - Binomial outcome: Absence of gestational sac on transvaginal ultrasound examination on Day 3 follow up
 - o Binomial outcome: Need for additional dose of misoprostol within 30 days of treatment
 - Binomial outcome: Need for uterine aspiration within 30 days of treatment
- Side Effects/Adverse Events
 - Side Effects Binomial Outcomes (N, %)
 - Fatigue
 - Headache
 - Dizziness or lightheadedness
 - Chills
 - Nausea
 - Diarrhea
 - Vomiting
 - Severe cramping
 - Fever
 - Other
 - Adverse Events Binomial Outcomes (N, %)
 - Excess bleeding requiring blood transfusion
 - Pelvic infection requiring antibiotics
- Patient Acceptability
 - Likert Scale Ordinal Outcomes (Median, Counts)

- Would you use this combination of medications again if you had another early pregnancy loss?
- Would you recommend this combination of medications to a friend with early pregnancy loss?
- If it was possible to take the first medication at home (versus in clinic), would you be more or less likely to use this combination of medications again?
- If it were possible to take the first medication at a different time (versus during your appointment), would you be more or less likely to use this combination of medications again?

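### No symptom checklist is planned before dosing, so pregnancy symptoms already present on Day 0 may be counted among the side effects in section 9.4.3

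*Combined protocol and SAP*

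**What the plan says.** The Schedule of Activities (section 1.3) marks the "Side effects and adverse events questionnaire" at Visit 2 (Day 3), Visit 3 (Day 8) and Visit 4 (Day 30), with no mark at Screening or Enrollment. A separate row, "Adverse event review and evaluation", is marked at Screening as well as at Visits 2, 3 and 4.

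The visit descriptions in section 4.1 agree. At Visit 1 the only form the participant fills in is demographic: "Participant completes paper baseline demographic questionnaire". For the follow-up visits the text is: "Participant fills out questionnaire regarding bleeding symptoms and any side effects or adverse events after taking the ulipristal acetate and misoprostol".

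Section 9.4.3 lists the symptoms under a line that begins "Side Effects Binomial Outcomes (N" and gives number and percentage for each. It does not define a side effect as new or worsened since baseline.

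Section 8.3.4 has a baseline rule for adverse events: "Any medical condition that is present at the time that the participant is screened will be considered as baseline and not reported as an AE". A condition that then deteriorates is recorded as an adverse event. Section 9.4.4 reports the 9.4.3 items by frequency and percentage, and adds severity and relatedness for other adverse events. Section 4.2 states that there is no comparison group. Section 5.5 confirms that every recruit is pregnant, with a loss already diagnosed.

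**The concern.** Some checklist items, such as nausea, vomiting, fatigue, headache and dizziness, can plausibly be present in early pregnancy before any drug is given. A yes on Day 3 may then mean that the symptom began after treatment, or that it was there all along. With one arm and no Day 0 answer, the planned tables cannot tell the two apart.

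Side effects are a stated secondary objective, and this pilot is meant to inform a larger trial. If existing symptoms enter the tally, the regimen will look less well tolerated than it is on those items. The plan would set them against quoted UPA rates of 18% for headache and 12% for nausea (sections 2.3.1 and 8.3.5). A Day 0 symptom state cannot be reconstructed reliably once UPA has been taken.

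**Working it through.** The plan states no figure on this point, so there is nothing to reproduce. The check sets the sections side by side and then bounds the possible bias.

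**1. Is there a pre-dose symptom record?** The Screening adverse event review is a pre-dose enquiry, but no symptom list is described for it. Under section 8.3.4 a symptom present at screening is not an adverse event, and reportable events are those that start after consent. A woman who already has nausea therefore generates no adverse event entry, and nothing says her nausea is written down elsewhere.

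**2. Does the baseline rule reach the checklist?** There are two readings.
- The checklist symptoms are adverse events. Section 8.3.5 supports this, since it discusses headache, nausea, fatigue and dizziness under adverse event reporting. The rule then applies, but it needs a Day 0 value for each symptom, and none is planned.
- They are a separate class. Section 9.4.3 supports this, since it lists side effects and adverse events under different sub-headings. The rule then does not reach them.

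Either way the gap remains.

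**3. Does anything else remove the background?** Clinician relatedness (section 8.3.3.2) is promised in the reporting only for adverse events outside the 9.4.3 list. There is no comparator.

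**4. How large could the bias be?** Let b be the share of women with the symptom on Day 0, and u the share of those women who tick it later although it has not worsened.

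Excess of the any-report percentage over the new-or-worsened percentage = b × u.

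Since u lies between 0 and 1, the excess lies between 0 and b. With b = 20%, it is 0 points at u = 0, 10 points at u = 0.5 and 20 points at u = 1.

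For the upper end (u = 1, none worsened), let t be the new-onset rate among women without the symptom on Day 0. Tally = b + (1 − b) × t, and new onset among all women = (1 − b) × t. For illustration, t is 12% for nausea and 18% for headache, the figures in section 2.3.1. Every b is an assumption.

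| Assumed b | Nausea tally | Nausea, new | Headache tally | Headache, new |
|---|---|---|---|---|
| 0% | 12.0% | 12.0% | 18.0% | 18.0% |
| 10% | 20.8% | 10.8% | 26.2% | 16.2% |
| 20% | 29.6% | 9.6% | 34.4% | 14.4% |
| 30% | 38.4% | 8.4% | 42.6% | 12.6% |
| 50% | 56.0% | 6.0% | 59.0% | 9.0% |

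Worked case: b = 20%, nausea: 0.20 + 0.80 × 0.12 = 0.296, of which 0.20/0.296 = 68% is pre-existing.

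**5. Would the confidence interval reveal it?** With 40 participants, 12% is nearest to 5 of 40, exact 95% interval 4.2% to 26.8%. The tally at b = 10% (20.8%) lies inside that interval. A modest background would therefore be smaller than the sampling error and invisible in the results. Section 9.3 restricts the main secondary analysis to adherent completers, so 40 is the largest possible denominator.

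**The case against.** The best defence is that the plan already has a baseline rule and a scheduled pre-dose review. On a fair reading the checklist symptoms are adverse events: the definition in section 8.3.1 is broad, and section 9.4.4 refers to the 9.4.3 list when it describes adverse event reporting. The weakness is then a missing cross-reference and a missing form. This has force, but the rule still lacks item-level data to work on.

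A reader might infer that the plan does count existing symptoms as side effects. The documents do not support that. The questionnaire itself is not among them, and it is described as asking about events after taking the drugs. Its items may ask only about new symptoms, in which case u could be near zero.

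A reader might also take one row of the table as the expected bias. That is not supported either. No background prevalence is given, least of all for women with a diagnosed loss. The 12% and 18% come from emergency-contraception data and allow nothing for misoprostol or for the dose studied here.

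Nor is it a defect that UPA and misoprostol are not separated on the form. The outcome in section 3 is for the combination, adverse event forms record time of onset, and misoprostol time is collected.

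Finally, the secondary aims are hypothesis-generating with no formal testing (sections 9.1 and 9.4.1). Overstating side effects is the cautious direction for safety, and a later randomized trial (section 6.3) would share the background between arms. All of this stands. It limits the importance of the point but does not make the pilot's percentages interpretable.

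**Conclusion.** The point holds as a gap in data collection and definition. No structured pre-dose symptom record is described, section 9.4.3 has no new-or-worsened definition, and the existing safeguards are not connected to the checklist. Existing symptoms may be counted, and if they are, the bias is upward.

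Its size is unknown. It is bounded by zero and the pre-dose prevalence of each symptom, and it depends on how the form is worded and how women answer. It concerns the items that plausibly occur in early pregnancy (a clinical assumption, not stated in the documents). Chills, fever, diarrhea and severe cramping are less obviously affected. Recruitment, adherence and retention are untouched.

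**What to change.** - Section 1.3 and section 4.1, Visit 1: give the same symptom checklist after consent and before UPA, for example within the Screening adverse event review, and add an X to the questionnaire row.
- Section 8.3.4 or 9.4.3: state that the baseline rule applies to the 9.4.3 symptoms.
- Section 9.4.3: report each symptom as new or worsened since Visit 1, beside the any-report percentage. A yes/no item shows what is new but not what is worse, so for symptoms ticked at Visit 1 the later forms should ask whether they have become worse. Show a missing Day 0 answer as its own category, as section 9.4.1 already provides.
- Optional: use the recorded onset time and misoprostol time to show which symptoms began before misoprostol.

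The cost is about two minutes of participant time at a visit already held, a follow-up question on worsening, and one more table column. No treatment or visit changes. It needs to be in place before dosing, because later participants can supply a Day 0 answer and those already dosed cannot.

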2 INTRODUCTION

2.1 STUDY RATIONALE

Early pregnancy loss affects approximately 10% of women throughout their reproductive lives [1]. Options for management of early pregnancy loss include expectant management, medical management, or surgical management. Data from two large randomized controlled trials suggests that pretreatment with mifepristone 200mg, a selective progesterone receptor modulator, prior to administration of misoprostol 800mcg increases effectiveness of medical management of early pregnancy loss and decreases the need for subsequent surgical management [2,3]. However, mifepristone is subject to regulations based on the FDA Risk Evaluation and Mitigation Strategy (REMS) restrictions that have remained in place for more than 20 years despite extensive safety data for mifepristone and evidence-based protocols for its use. Many OBGYN and non-OBGYN providers do not prescribe mifepristone due to these logistical barriers. Ulipristal acetate (UPA) is another selective progesterone receptor modulator that may allow for similar priming of the endometrium and sensitization of the myometrium to the prostaglandins to improve effectiveness of misoprostol in medical management of early pregnancy loss.

Ulipristal acetate is not subject to the FDA REMS restrictions and is available as a prescription medication through commercial pharmacies, with approximately 72% of pharmacies able to fill the prescription within 24 hours [4]. Thus, utilizing UPA plus misoprostol for early pregnancy loss may improve access to patients who otherwise may not be prescribed mifepristone. We propose a pilot feasibility study of UPA plus misoprostol for medical management of early pregnancy loss to assess if a larger clinical trial would be possible.

2.2 BACKGROUND

Early pregnancy loss (EPL), defined as a nonviable intrauterine pregnancy, occurs in approximately 10% of clinically recognized pregnancies [1]. Early pregnancy loss encompasses both anembryonic gestations (presence of an empty gestational sac without embryo or fetus, previously known as a "blighted ovum") and embryo or fetus without fetal cardiac activity before the 13th week of gestation [1]. Often, early pregnancy loss is diagnosed on viability ultrasound, and specific radiologic criteria have been laid out by the Society of Radiologists in Ultrasound Multispecialty Consensus Conference (so called "Doubilet criteria", see Appendix A) [5]. When faced with this diagnosis, women are offered expectant management, medical management, or surgical management to allow expulsion of the pregnancy. Misoprostol, a prostaglandin analogue, has long been the standard of care for medical management of EPL; however, recent randomized controlled trials of mifepristone use prior to misoprostol illustrated increased rates of pregnancy expulsion with medication alone and decreased need for surgical intervention to complete evacuation of the pregnancy [2,3]. As a selective progesterone receptor modulator (SPRM) with antagonist effects on the endometrium and myometrium, mifepristone increases uterine contractility and sensitizes the myometrium to prostaglandin use, allowing for a lower dose of misoprostol to cause uterine emptying and shorter time to pregnancy expulsion. Following treatment with mifepristone, endometrial cells exhibit an increase in decidual prostaglandin release and decreased activity of prostaglandin dehydrogenase to prevent metabolism of prostaglandins [6]. Further, mifepristone downregulates progesterone receptor signaling in the endometrium, prompting antiproliferative effects that halt secretory changes to the endometrium and decrease endometrial receptivity [7,8].

While mifepristone exhibits many benefits when used for EPL, availability of mifepristone is limited by the Risk Evaluation and Mitigation Strategy (REMS) FDA restrictions [9]. This program restricts mifepristone administration to certified providers, requires a patient agreement form to be signed prior to administration, and requires administration of the medication in the presence of the certified provider [10]. These restrictions have been in place since mifepristone was FDA-approved in 2000 despite excellent safety data and evidence-based protocols; even with extensive legislative appeals to remove the REMS restrictions [11]. Particularly as many women diagnosed with EPL are seen in non-OBGYN settings such as the emergency department or primary care, these restrictions often prevent patients from accessing appropriate evidence-based medical management. Indeed, in a large qualitative survey of primary care clinicians, two thirds of providers were unable to dispense mifepristone in their clinics for medication abortion or EPL care, with most citing logistical difficulties with the REMS restrictions and resistance from health center leadership as rationale [12]. Logistical barriers to prescribing mifepristone for medication abortion has also been well documented among both OBGYN and non-OBGYN providers [13,14].

Ulipristal acetate (UPA, Ella®) is another substituted steroid synthetic progesterone agonist/antagonist commonly used for emergency contraception with a similar molecular weight, structural formula, and molecular formula to mifepristone [15-17]. As a class, progesterone receptor modulators are utilized in

similar clinical scenarios ranging from contraception to treatment of fibroids, endometriosis, and other causes of heavy or irregular bleeding. In the normal menstrual cycle, progesterone from the corpus luteum transforms the proliferative endometrium to the secretory endometrium for implantation. In contrast, the presence of SPRMs causes the endometrium to undergo glandular dilation and antiproliferative effects [18]. Like other SPRMs, UPA induces changes in the endometrium including a significant increase in glandular dilation and architecture and decrease in endometrial thickness similar to the effects noted following administration of mifepristone [19,20]. UPA's effect on endometrial cells is also responsible for similar changes in receptivity markers when compared to mifepristone [21,22]. With the similarities between UPA and mifepristone, a recent pilot study investigated UPA in place of mifepristone for cervical preparation prior to dilation and evacuation for termination of pregnancy between 16- and 18-weeks' gestation and found that UPA was a feasible and acceptable alternative [23].

While mifepristone is an effective medication for EPL, prescribing restrictions limit the ability of patients to use this medication to increase the efficacy of medical management of EPL. Thus, alternative regimens are needed to increase access to effective medical management of EPL for women choosing medical management. Given similarities between UPA and mifepristone, we propose utilizing UPA prior to misoprostol for medical management of EPL. As no prior studies have investigated UPA for this use, we propose a pilot feasibility study of UPA plus misoprostol for medical management of EPL to inform a subsequent larger clinical trial if successful.

